The resulting effect of this integrated synergy will be to promote greater functional gains (primary hypothesis) at the end of 12 weeks of home- based exercise training and to promote better maintenance of the benefits of pulmonary rehab at 24 weeks than in the no-music group (secondary hypothesis).

C.1.2. General Overview of Design. The proposed study has been designed as a randomized, controlled clinical trial in which COPD patients will be randomized into an exercise program with RAS-enhanced music (RAS- music group) or in an exercise program without music (no-music group). COVID 19 patients will be randomized into an exercise program with RAST-enhanced music (RAST- music group and strength training) or in an exercise program without music (no-music but will have strength training group). Patients will complete testing procedures at pre-randomization, at 6 weeks, immediately post-rehabilitation, and 24 weeks after enrollment. Testing at 6 weeks is included to provide interim follow-up should patients not complete the 12 weeks of training.

C.1.3. Sample Size Calculation.

Sample size was estimated based on a 2-group mixed model design with baseline, 6 and 12-week measurements. Our primary goal is to compare the difference in distance walked during the standard 6MWT over 12 weeks between groups (see **C.1.9.1.a.**). We estimate that the COPD target sample size of 68 patients per group completing 12 weeks will ensure 80% power to detect the differences between treatment arms using a two-sided significance level of 0.05, assuming a correlation of 0.70 between measurements. These estimates are based on our PAD pilot data and include similar standard deviations at baseline and at 6 weeks between groups and over time (232 feet), correlations between measurement of 0.76 to 0.86, and an increase of 87.2 feet at 6 weeks for the RAS- music group, with a slightly higher level for those completing the 12-week assessment. Based on the work of

Table. 2 COPD Study inclusion and exclusion criteria

Inclusion Criteria	Exclusion Criteria
• ≥ 40 yr. of age	• Respiratory infection/COPD exacerbation within the previous four weeks
• FEV ₁ ≤ 70%	• Exercise-limiting heart disease (Congestive heart failure – i.e., New York Heart Association Class III or IV; positive stress test or other indicators of heart disease or complaints of angina during the stress test)
• FEV ₁ /FVC <70%	• Exercise-limiting peripheral arterial disease (stops walking due to intermittent claudication)
• Mean SpO ₂ ≥ 88% at peak exercise (with or without oxygen supplementation)	• Stops exercise for arthritic pain in knee or hips
• Ability to hear music	• Inability to walk on the treadmill
	• Any unforeseen illness or disability that would preclude exercise testing or training
	• Participation in a formal exercise program within the previous 12-weeks

Liu et al.,¹¹ we estimate no change in the 6MWT in the no-music exercise training group.

COVID 19 sample size was estimated based on a 2-group design with pre- and post-test measurements. Our primary goal is to compare the difference in distance walked during the *standard 6MWT* at 12 weeks between groups. We estimate that over a two-year period we will ensure complete data collection on a total of 72 patients (36 per group). This will ensure a 58% power to detect the differences between treatment arms using a two-sided significance level of 0.05, assuming a correlation of 0.65 between measurements. Our pilot data used to support this estimate include the most conservative correlation observed between measurements ($r=0.65$), and an increase of 41 meters at 12 weeks for the intervention group.

According to the local IRB, enrollment is the equivalent to a patient signing an informed consent. In our three latest studies,^{3,4,94} 30% of patients who signed the informed consent (i.e., enrollees) did not meet pulmonary function criteria or did not qualify for other reasons.⁹⁵ Moreover, based on our previous work, we expect an attrition 12 weeks after randomization of about 8%, and an attrition 24 weeks after randomization of 20%. Accordingly, to have complete data in 136 COPD patients as required by our power calculation (see above), we plan to 'enroll' 243 COPD patients (i.e., signed informed consent) expecting to 'randomize' 170 of them, and to lose 34 of this latter group by week 24 (end of the study). We will enroll 100 patients with COVID 19 into this study.

C.1.4. Recruitment. COPD patients will be recruited from the outpatient Pulmonary Medicine Service at the Hines VA (Tab. 2). COVID 19 patients will be recruited from Hines outpatient Medical Services. No patient will be excluded based on gender or ethnicity. About 8 patients per month will be 'enrolled' with 5-6 of them being randomized. This will allow us to meet our target sample over 3.5 years (Tab. 3). Recruitment will be monitored weekly. We are confident we will meet the target number of participants (see also section C.5. Potential Problems) considering we enrolled more than 1000 patients into our various investigations^{3,4,81,82,96} and that many patients with COPD attend Hines VA (4,803 unique patients with an ICD10-COPD code in FY2016, which is an underestimation of more than 1000 patients as this number does not capture patients in whom the ICD 9-COPD code has not been updated to the ICD 10-COPD code).

C.1.5. Screening and Baseline Testing.

Proposed study participants will be screened for eligibility and written informed consent will be obtained. All testing will take place at Hines

Table. 3 Recruitment and randomization schedule

	Year 1	Year 2	Year 3	Year 4
Number of enrolled patients	50	80	80	33
Number of randomized patients	55	55	25	

VAH's Physical Performance Research Laboratory. During screening, patients will be asked about their medical history and medication use. This will be followed by physical examination, pulmonary function testing and completion of quality of life/dyspnea questionnaires (Tab. 4). Eligible patients will perform additional baseline tests⁴ that include a functional assessment of the quadriceps (after the completion of 12 weeks of training), quadriceps ultrasonography, two *standard 6MWT* (according to ATS recommendations, patients will be instructed to walk as fast as they can without running)⁹⁷ and two *modified 6MWT* at their usual/leisurely walk pace (*leisurely-paced 6MWT*; see section C.1.9.1). Walking cadence during these tests will be used to adjust the RAS exercise prescription (RAS-music group). In addition, data from the *standard 6MWT* will be used to test the primary hypothesis that exercise training with RAS-music elicits greater increases in *standard 6MWT* distance than exercise training alone (see sections C.1.6.1. and C.1.9.1). Patients will receive an Actigraph to measure physical activity over the course of one week.

After baseline testing is completed (Tab. 4) and study criteria are met, COPD patients will be randomized to exercise training with RAS-enhanced music (RAS-music group) or exercise training without music. COVID 19 patients will be randomized to exercise training with RAST-enhanced music and strength training (RAST-music group) or exercise training without music and with strength training. We chose a no-music control group as opposed to music without RAS-enhancement not to contaminate the control group. Music

can have strong bass or, when listening to music, individuals can augment the bass. Strong bass could provide an unintended RAS-like intervention. Testing and measures are described in sections **C.1.9.1 t**

COVID 19 Inclusion/Exclusion Criteria

Inclusion Criteria

- ≥ 18 yrs. of age
- Previous hospital and/or emergency room visit for laboratory-confirmed COVID-19 diagnosis.
- Able to walk independently
- Mean SpO₂ ≥ 88% at peak exercise (w/ or w/o O₂)
- Ability to hear music

Exclusion Criteria

- Able to walk more than 550 meters during a standard 6-minute walk test
- Exercise limiting heart disease (complaints of angina during the 6- minute walk distance tests or other indicators of exercise-limiting heart disease)
- Congestive heart failure (New York Heart Association Class III or IV)
- Exercise-limiting peripheral arterial disease (stops exercise due to intermittent claudication)
- Stops exercise due to arthritic pain in the knee or hips (self-report)
- Pregnancy

C1.9.5.

Randomization will be computer-generated with permuted blocks with random block sizes. This strategy is intended to preserve balance in the randomization of patients as to maintain unpredictability of the treatment assignments. Group assignment will be managed by the Hines Cooperative Studies Program Coordinating Center (CSPCC). When a patient is ready for randomization, we will contact the CSPCC to receive the randomization designation. To maintain testing integrity, [name], [name] or their designee will supervise patient testing and will be blinded to group assignment. When data are reviewed, the data will be void of any identifiers. [name] (PI, pulmonologist) will remain blinded to group assignment. If patients develop medical problems during the study [name] can request to be unblinded. When unblinded, the two physicians will not supervise further exercise testing for those given

patients. The exercise physiologists, will assist with follow-up exercise, and will ask patients standardized questions regarding dyspnea, angina and ability to continue exercising.⁹⁸ She will be blinded to group assignment. The project manager ([name]) and exercise physiologist ([name]) and the statistician ([name]) will be aware of patient's group assignment.

Exercise Prescription. Upon randomization, all patients will receive a 1-hour educational session on exercise rehabilitation.

Specifically, the clinical exercise physiologist will work with patients to: (1) set up a schedule that fits with

Table. 4 Testing schedule

	Measure(s)	Screen/ Baseline	6- wks	12- wks	24- wks
Eligibility/Screening					
• FEV ₁ ≤ 70% FEV ₁ /FVC <70%	Pulmonary function test	x			
• Eligibility	History, Mini-Mental test	x			
• Co-morbidities	Charlson Index	x			
• Demographics	Demographic data information	x			
• Usual/leisurely walking cadence	Leisurely-paced 6MWT	x			
Primary Dependent Variable					
• Walking distance	Standard 6MWT	x x	x	x	x
Secondary Dependent Variables and Independent Variables					
• Dyspnea onset • Exercise duration (Treadmill walking time)	Constant-load treadmill test	x x	x	x x	x x
• QoL, Dyspnea, Self- efficacy, Physical Function	Questionnaires (SF-36, CRQ, Self-efficacy for walking) COVID 19 CAS	x	x	x	x
• Adherence	Fitbit Step Counts	x	x	x	x
• Daily physical activity	Step counts	x	x	x	x

Definition of abbreviations: 6MWT = six minutes walk test; QoL = quality of life

the patients' schedule for home-based exercise by with his/her usual daily schedule; (2) identify time-slots for exercise; (3) provide information on exercise tips; (4) address perceived barriers to exercise, (5) provide contact information, and (6) build a relationship with patients to provide support and identify health concerns.

C.1.6.1 Exercise Prescription:RAS/RAST-music group

C.1.6.1.a. Music selection: *Immediately after randomization, COPD patients in the RAS-music group will be asked to list 15 songs/music pieces within the one or more genres they most enjoy. If patients need help naming songs/music pieces, we will present them with a catalogue of "Top Twenty" songs/music within several genres. Patients will be also informed that they can choose songs/music not listed in the catalogue.*

COVID 19 patients in the RAST music group will meet with a music therapist at baseline and other timelines to complete their music assessment and music choices.

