A.3.1.2. Exercise Limitation in COPD: Limb Muscles. Reduced muscle mass (sarcopenia) is a major systemic manifestation of COPD, and is present in up to one-third of patients.^{32,34} Sarcopenia is associated with muscle weakness,³⁵ decreased exercise tolerance,³⁶ worse quality of life³⁶ and decreased survival.³⁴ Lower extremity sarcopenia is independent of body mass index (BMI),³⁷ highlighting the importance of direct assessment of muscle dimensions through imaging techniques such as ultrasonography, as now planned.^{38,39} Additional factors contributing to decreased exercise tolerance include decrease in fatigue-resistant type 1 muscle fibers, increase in type 2 fatigue-sensitive fibers, decrease in oxidative enzymes and increase in glycolytic enzymes (quadriceps).³⁷ Presently, exercise training is the only strategy that can improve these structural and metabolic abnormalities in most patients with COPD.^{28,37,40}

We propose to collect baseline and follow-up data on rectus femoris size (ultrasound) reasoning that these data will shed light into the impact of muscle size and function on the response to our rehabilitation program. These data will be used also to explore whether there are specific subgroups of patients who – in addition to RAS/RAST-enhanced exercise-training – could benefit from specific ancillary interventions (see sections **C.4. Alternative Outcomes** and **C6. Future Directions**).⁴¹

A.3.2. Exercise-training. Exercise-training is a critical intervention in the pulmonary rehab of patients with COPD⁴² that can produce positive clinical outcomes.^{3,4,6,7,9,43}

A.3.2.1 Exercise-Training: Impact of Locomotor Muscle Response. To obtain physiological training adaptations in a skeletal muscle, the level of load during training must be sufficient to stress the muscle and cause contractile fatigue (*muscle overload*).^{44,45} In a study by Burtin et al,⁴⁴ 29 of 46 patients with COPD developed quadriceps fatigue during a scheduled rehab visit; after 3 months of training, fatiguers achieved greater training in terms of exercise capacity and health-related quality of life than non-fatiguers. Similar results were reported by Mador et al.⁴⁵

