In the investigations of Burtin et al⁴⁴ and Mador et al,⁴⁵ quadriceps fatigue was objectively quantified by recording decreases in force of knee extension elicited by single magnetic stimulations of the femoral nerve (quadriceps twitch or Quad-Tw)(**Fig. 2**). We have extensively used this state-of-the-art technique to evaluate strength and fatigue in healthy volunteers, patients with COPD and mechanically ventilated patients.¹³¹

We will collect data on quadriceps fatigability at the end of training (Quad-Tw). Specifically, we will determine whether randomization into RAS-music will increase the likelihood of quadriceps fatigue and whether quadriceps fatigue contributes to the beneficial effects of the home-based, RAS-music exercise program. These data will be used also to explore whether there are specific subgroups of patients who – in addition to RAS-enhanced exercise-training – could benefit from specific ancillary interventions (see sections **C.4. Alternative Outcomes** and **C6. Future Directions**).⁴¹

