B.5. Is Systemic Inflammation a Mechanism of Functional Impairment in COPD? (VA Resp-011-06F). This investigation was designed to test the hypothesis that in patients with COPD, greater functional impairment is associated with higher levels of circulating inflammatory cytokines and greater oxidative stress.

Two unique experimental modalities used in the VA Resp- 011-06F study that are relevant to the current proposal are: (a) assessment of quadriceps fatigue and (b) assessment of quadriceps muscle dimensions. We will separately describe preliminary results pertaining to these two modalities.

a-Quadriceps fatigue: To determine whether patients developed quadriceps fatigue after exercise, maximal voluntary contractions (MVC) and quadriceps twitch force elicited by magnetic femoral nerve stimulation (Quad-Tw) were recorded in 63 patients before and after constant-load cycle ergometry. Fatigue (decrease in Quad-Tw > 15% of baseline values, **Fig. 2**)⁴³ occurred in 67% of patients. Independent predictors of exercise-induced quadriceps fatigue were: less quadriceps recruitment, smaller pre-exercise Quad-Tw, greater inflammation (hsCRP, IL-6), and greater workrate ($p \leq 0.05$).⁹²

b-Quadriceps dimensions: In the same 63 patients, the cross-sectional area of the rectus femoris using ultrasonography³⁹ was identified as an independent predictor of exercise capacity (VO_2 max and Watts max).

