Two, RAS-music adds nothing to gains achieved with exercise-training alone. Two mechanisms could cause this unlikely^{11,58} result: (1) insufficient stress on muscles and (2) suboptimal entrainment. The first possibility would be supported if prevalence of exercise-induced quadriceps fatigue elicited by a typical exercise-training session in the two groups is the same. The second possibility would be supported if less gains are related to greater failure to entrain gait during teaching sessions (*poor entrainers*). If that happens, we plan future studies where RAS-music in *poor entrainers* will be optimized – i.e., in the subgroup of *poor entrainers* we will increase the volume of RAS music and augment the entraining pulse (strongly emphasized beat) to facilitate music-motor synchronization.²⁷

Three, the positive impact of RAS-music is smaller than predicted – i.e., Type II error.

C.4.3. Alternative Outcome #3. Neither group experiences improvement in 6-minute walking distance. If this occurs at least three possibilities must be considered.

One, neither group engaged in home-based exercise training. Several factors, including psychological phenotype (i.e., anxiety, depression)¹²² are known to reduce acceptance and adherence to rehab.^{7,8,12,57,58} If our data demonstrate that psychological factors interfere with acceptance and adherence to home rehab (see *Explorative Objective*), we will plan a future investigation that will include formal psychological interventions (i.e., cognitive behavioral therapy) to address those factors.¹²³

Two, physiological/clinical factors decreased exercise tolerance thereby curbing intensity of exercise during training.⁶³ These factors could include frequency of exacerbations, severity of lung disease, quadriceps dimension, recruitment and strength, systemic inflammation (hsCRP) (see *Explorative Objective*).⁶⁴ If the negative results of our study parallel these physiological/clinical factors, we will explore the possibility of combining pulmonary rehab with the administration of novel anti-inflammatory agent(s). This strategy is based on the mounting evidence that systemic inflammation may contribute to local and systemic manifestations of COPD.¹²⁴ Additional ancillary interventions could include strategies to enhance muscle anabolism,^{125,126} to enhance muscle recruitment by the central nervous system,¹²⁷ and strategies to promote muscle overload (fatigue) during training.^{41,128}

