C5.2. Exacerbations. Exacerbations can cause functional impairment and decreased peripheral muscle function (see sections **A.3.4** and **C.2.3. Exploratory Objective**). Exacerbations will be tracked as part of our data safety monitoring.

C.5.3. Adherence to the home-based program. In our studies, patient compliance to training has ranged from 90 to 95%.^{3,4,94} In this proposal we will take several steps to ensure high compliance with training (see **C.1.7.**).¹³⁹ All patients will receive at weekly phone calls. In addition, they will be called if they do not sync their Fitbit or do not exercise for three consecutive sessions. Additionally, patients will receive \$20 to cover travel expenses for each visit to the lab.

C.6. Future Directions. If, as we hypothesize, RAS-music plus exercise-training improves exercise capacity at the conclusion of a 12-week home-based rehab program and, thereafter, it promotes the maintenance of physical activity, three questions for future studies will arise: (1) What is the effect of RAS-music plus exercise on the systemic manifestations of COPD including depression, osteoporosis, and coronary artery disease? (2) Could RAS-music plus exercise decrease the staggering health care cost for veterans and non-veterans with COPD?

(3) What is the effect of RAS-music plus exercise on survival? To address these questions, we will pursue a multi-center randomized clinical trial. In addition, we will consider additional studies tailored to specific subgroups of patients. For example, if we find that to achieve and maintain benefits from home-based, RAS-music rehab patients must also develop quadriceps fatigue,^{44,45} we will design an investigation where in “*non-fatigues*” we will combine RAS-music plus a one-leg exercise-training^{41,128} or RAS-music plus neuromuscular electrical stimulation of the quadriceps, gastrocnemius and tibialis anterior muscles.¹²⁶

Risk to Subjects

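### The arms are to be compared on quadriceps fatigue as a yes/no state, although twitch force gives a continuous fall; under stated assumptions this costs roughly 15 to 27 points of power on an exploratory mechanism question

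*Combined protocol and SAP*

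**What the plan says.** The measure is continuous. Section A.3.2.1, describing the cited rehabilitation studies, says that "quadriceps fatigue was objectively quantified by recording decreases in force of knee extension elicited by single magnetic stimulations of the femoral nerve". It then states the trial's own question: "we will determine whether randomization into RAS-music will increase the likelihood of quadriceps fatigue", together with whether fatigue contributes to the benefit of the music programme.

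C.4.2 covers the case in which the walking-distance gains are similar in the two arms. Insufficient stress on the muscles is to be "supported if prevalence of exercise-induced quadriceps fatigue elicited by a typical exercise-training session in the two groups is the same". C.6 plans follow-on work if, to benefit, "patients must also develop quadriceps fatigue", with a separate study for those who do not.

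The only numerical definition of fatigue is in B.5(a), a report of earlier work: "decrease in Quad-Tw > 15% of baseline values". There, after constant-load cycling in 63 patients, fatigue "occurred in 67% of patients". A.3.2.1 also cites a study in which "29 of 46 patients with COPD developed quadriceps fatigue during a scheduled rehab visit".

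C.2.3 lists quadriceps fatigue among the independent variables of two exploratory models. It does not say whether fatigue enters as yes/no or as the continuous fall. C.2 contains no between-arm test of fatigue, and no effect size or power is given for one. Under C.1.6.1, Quad-Tw is recorded at week 12 only.

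**The concern.** Likelihood and prevalence are properties of a yes/no state. Cutting the percentage fall at 15% treats a 16% fall and a 45% fall as the same result. If most control patients are already above the cut, as in the two earlier groups, additional fatigue in the music arm has limited room to show.

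The direction of the error matters because of the C.4.2 rule. Similar prevalence is taken to support one explanation of a null walking result: that the muscles were not stressed enough. A comparison with low power returns no clear difference more often, including when muscle load truly differed. The trial could then attribute a null result to insufficient stress and plan follow-on studies on that basis. Quad-Tw is measured once, so there is no second opportunity.

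**Working it through.** **The plan's own calculation.** The only fully specified calculation is for COPD walking distance (C.1.3): 68 per group, 80% power, two-sided 0.05, SD 232 ft, correlation 0.70, and a gain of 87.2 ft against none.

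- SD of change = 232 × √(2 × (1 − 0.70)) = 179.7 ft.
- n = 2 × [179.7 × (1.960 + 0.842) / 87.2]² ≈ 67 per arm; power at 68 per arm is 80.8%. The figure reproduces.

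I use 68 per arm for the fatigue comparison.

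**Inputs for the fatigue comparison.**

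- Control prevalence p₀: 67% (B.5) or 29/46 = 63% (A.3.2.1). That either applies to this trial is an assumption.
- Percentage fall in Quad-Tw: normal, equal SD in both arms (assumption).
- True shift d, in SD units: 0.2 to 0.8 (assumption).

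**Formulas** (Φ is the standard normal distribution function).

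- Continuous scale: power ≈ Φ(d√(n/2) − 1.96).
- Yes/no scale: p₁ = Φ(Φ⁻¹(p₀) + d). With p̄ the mean of p₀ and p₁, power = Φ[(p₁ − p₀ − 1.96 s₀)/s₁], where s₀ = √(2p̄(1 − p̄)/n) and s₁ = √([p₀(1 − p₀) + p₁(1 − p₁)]/n).

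**Worked case**, p₀ = 0.67, d = 0.484, n = 68.

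- p₁ = Φ(0.440 + 0.484) = 0.822; p̄ = 0.746.
- s₀ = √(2 × 0.746 × 0.254/68) = 0.0747; s₁ = √((0.2211 + 0.1463)/68) = 0.0735.
- Yes/no power = Φ[(0.1522 − 0.1463)/0.0735] = Φ(0.08) = 53%.
- The two-sample t-test has 80.0% power for the same shift, so the loss is 27 points.

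**Across shifts**, 68 per arm, normal approximation on both scales:

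| Shift (SD) | Continuous | Yes/no, p₀ = 63% | Yes/no, p₀ = 67% | Loss (points) |
|---|---|---|---|---|
| 0.2 | 21% | 14% | 14% | 7 |
| 0.3 | 42% | 26% | 25% | 15-16 |
| 0.4 | 65% | 42% | 40% | 23-24 |
| 0.5 | 83% | 58% | 56% | 25-27 |
| 0.6 | 94% | 72% | 70% | 21-24 |
| 0.8 | 99.7% | 91% | 89% | 9-11 |

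To regain 80% power at a shift of about 0.48 SD, the yes/no analysis would need about 123 per arm (p₀ = 63%) to 129 per arm (p₀ = 67%).

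**Dependence on shape**, simulated at 68 per arm, d about 0.48, p₀ = 67%, t-test against the two-proportion test:

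| Distribution of the fall | Continuous | Yes/no | Loss (points) |
|---|---|---|---|
| Normal | 80% | about 54% | 26 |
| Heavy-tailed (t, 5 df) | 80% | 63% | 17 |
| Gamma, right skew 0.5 | 80% | 65% | 15 |
| Gamma, right skew 1 | 80% | 81% | none |
| Gamma, left skew 1 | 79% | 42% | 37 |

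**The case against.** The strongest reply is that the plan specifies no dichotomised analysis. A.3.2.1 is background, C.4.2 is contingency discussion, C.2 has no between-arm fatigue test, and the 15% cut belongs to an earlier study. This stands in part. The 15% cut is implied for this trial, not adopted, and C.2.3 leaves the form of the variable open. But both places that state the between-arm question put it in yes/no terms, C.4.2 draws an inference from the answer, and nothing plans a comparison of the continuous fall.

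The size is also open to challenge, and that stands. The shift and the distribution are assumed. The 67% followed cycling, whereas C.4.2 concerns a typical training session, which here is walking progressed subject to a dyspnea limit. At a control prevalence of 50% the loss at 0.484 SD is still about 20 points (80% to 60%), but a ceiling is then not the cause.

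Next, A.3.2.1 gives a threshold rationale: training must load the muscle enough to cause contractile fatigue. Whether a patient reached overload is a yes/no question that a mean difference does not answer. This stands, and it is a reason to report both scales.

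Finally, reading sameness from a non-significant test is a fault on either scale. This also stands; changing the scale alone would not cure it.

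A reader might go further and infer that the models relating fatigue to walking gain discard information too, since a 67/33 split of a normal variable keeps only about 59% of its explained variance. The documents do not support that as a criticism, because C.2.3 never says the variable is split.

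**Conclusion.** The concern holds as a minor point about an exploratory question. The plan frames the between-arm fatigue comparison as yes/no when a continuous fall is available from the same recordings. With 68 per arm, a roughly normal fall, 63-67% control prevalence and a true shift of 0.3-0.6 SD, the cost is about 15 to 27 points of power. It is about 7 points at 0.2 SD and 9 to 11 at 0.8 SD. With skewness of 1 in either direction, it runs from none to about 37.

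Two stronger readings are tempting and are not supported. One is that the loss is a fixed 15 to 30 points whatever the data look like; without an SD, effect size or distribution in the documents, only a conditional range can be given. The other is that the trial's main conclusion is at risk. No COPD primary or secondary hypothesis uses fatigue, and the C.4.2 rule applies only after a null walking result, where fatigue is one of several explanations offered.

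**What to change.** - **A.3.2.1 and C.4.2:** make the main fatigue comparison the between-arm difference in mean percentage fall in Quad-Tw, from before to after the week-12 exercise session, with its 95% CI.
- **C.4.2:** replace the criterion that prevalence is the same with a reading of that estimate and its CI, not of non-significance. A CI that still admits a material difference in muscle load should not be taken as support for insufficient stress.
- **Both sections:** also report the proportion in each arm with a fall above 15%, and its CI, because the overload and non-fatiguer questions concern a threshold.
- **C.2.3:** state that fatigue enters the models as the continuous fall. This is a clarification, since its form is not given there.

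The cost is wording only. The percentage fall has to be calculated before any cut can be applied, so no new measurement, patient or visit is needed. The main result becomes slightly less directly comparable with the earlier fatiguer/non-fatiguer studies, which the retained proportion covers.
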